**TABLE 14.2-1.8.1 ANALYSIS OF MEAN CHANGE FROM BASELINE IN HV SDS (CS) BY COMPLETERS, TOTAL AND VISIT (FAS)**

See shell for TABLE 14.2-1.2.1 ANALYSIS OF MEAN CHANGE FROM BASELINE IN HEIGHT BY COMPLETERS, TOTAL AND VISIT (FAS).

Programming note: Please add one column 'Status' (value: Completers, Total) before column Visit.

**TABLE 14.2-1.8.2 ANALYSIS OF MEAN CHANGE FROM BASELINE IN HV SDS (CS) BY COMPLETERS, TOTAL, VISIT AND SEX (FAS)**

See shell for TABLE 14.2-1.2.2 ANALYSIS OF MEAN CHANGE FROM BASELINE IN HEIGHT BY COMPLETERS, TOTAL, VISIT AND SEX (FAS).

Programming note: Please add one column 'Status' (value: Completers, Total) before column Visit.

**TABLE 14.2-1.8.3 ANALYSIS OF MEAN CHANGE FROM BASELINE IN HV SDS (CS) BY, COMPLETERS, TOTAL, VISIT AND INITIAL TREATMENT (FAS)**

See shell for TABLE 14.2-1.2.3 ANALYSIS OF MEAN CHANGE FROM BASELINE IN HEIGHT BY COMPLETERS, TOTAL, VISIT AND INITIAL TREATMENT (FAS).

Programming note: Please add one column 'Status' (value: Completers, Total) before column Visit.

**TABLE 14.2-1.9.1 SUMMARY OF HV SDS (PC) BY COMPLETERS, TOTAL AND VISIT (FAS)**

See shell for TABLE 14.2-1.5.1 SUMMARY OF HEIGHT VELOCITY (HV) BY COMPLETERS, TOTAL AND VISIT (FAS).

Programming note: Please add one column 'Status' (value: Completers, Total) before column Visit. Please add confidence interval for means here.

**TABLE 14.2-1.9.2 SUMMARY OF HV SDS (PC) BY COMPLETERS, TOTAL, VISIT AND SEX (FAS)**

See shell for TABLE 14.2-1.5.2 SUMMARY OF HV BY COMPLETERS, TOTAL, VISIT AND SEX (FAS).

Programming note: Please add one column 'Status' (value: Completers, Total) before column Visit.

**TABLE 14.2-1.9.3 SUMMARY OF HV SDS (PC) BY COMPLETERS, TOTAL, VISIT AND INITIAL TREATMENT (FAS)**

See shell for TABLE 14.2-1.5.3 SUMMARY OF HV BY COMPLETERS, TOTAL, VISIT AND INITIAL TREATMENT (FAS).

Programming note: Please add one column 'Status' (value: Completers, Total) before column Visit.

**TABLE 14.2-1.9.4 SUMMARY OF HV SDS (PC) BY COMPLETERS, TOTAL, AND VISIT FOR PATIENTS WITH AND WITHOUT POSITIVE ANTI-RHGH ANTIBODIES (FAS)**

See shell for TABLE 14.2-1.5.2 SUMMARY OF HV BY COMPLETERS, TOTAL, VISIT AND SEX (FAS)

Programming note: Present patient with and without positive anti-rhGH antibodies instead of sex. Please add one column 'Status' (value: Completers, Total) before column Visit.

**TABLE 14.2-1.10.1 ANALYSIS OF MEAN CHANGE FROM BASELINE IN HV SDS (PC) BY COMPLETERS, TOTAL AND VISIT (FAS)**

See shell for TABLE 14.2-1.2.1 ANALYSIS OF MEAN CHANGE FROM BASELINE IN HEIGHT BY COMPLETERS, TOTAL AND VISIT (FAS).

Programming note: Please add one column 'Status' (value: Completers, Total) before column Visit.

**TABLE 14.2-1.10.2 ANALYSIS OF MEAN CHANGE FROM BASELINE IN HV SDS (PC) BY COMPLETERS, TOTAL, VISIT AND SEX (FAS)**

See shell for TABLE 14.2-1.2.2 ANALYSIS OF MEAN CHANGE FROM BASELINE IN HEIGHT BY COMPLETERS, TOTAL, VISIT AND SEX (FAS).

Programming note: Please add one column 'Status' (value: Completers, Total) before column Visit.

**TABLE 14.2-1.10.3 ANALYSIS OF MEAN CHANGE FROM BASELINE IN HV SDS (PC)  
BY COMPLETERS, TOTAL, VISIT AND INITIAL TREATMENT (FAS)**

See shell for TABLE 14.2-1.2.3 ANALYSIS OF MEAN CHANGE FROM BASELINE IN HEIGHT BY COMPLETERS, TOTAL, VISIT AND INITIAL TREATMENT (FAS).

Programming note: Please add one column 'Status' (value: Completers, Total) before column Visit.

**TABLE 14.2-2.1.1 SUMMARY OF IGF-1 SERUM LEVELS (NMOL/L) BY COMPLETERS,  
TOTAL AND VISIT (FAS)**

See shell for TABLE 14.2-1.1.1 SUMMARY OF HEIGHT BY COMPLETERS, TOTAL AND VISIT (FAS).

Programming note: Please add one column 'Status' (value: Completers, Total) before column Visit. Please add confidence interval for means here.

**TABLE 14.2-2.1.2 SUMMARY OF IGF-1 SERUM LEVELS (NMOL/L) BY COMPLETERS,  
TOTAL, VISIT AND SEX (FAS)**

See shell for TABLE 14.2-1.1.2 SUMMARY OF HEIGHT BY COMPLETERS, TOTAL, VISIT AND SEX (FAS).

Programming note: Please add one column 'Status' (value: Completers, Total) before column Visit. Please add confidence interval for means here.

**TABLE 14.2-2.1.3 SUMMARY OF IGF-1 SERUM LEVELS (NMOL/L) BY COMPLETERS,  
TOTAL, VISIT AND INITIAL TREATMENT (FAS)**

See shell for TABLE 14.2-1.1.3 SUMMARY OF HEIGHT BY COMPLETERS, TOTAL, VISIT AND INITIAL TREATMENT (FAS).

Programming note: Please add one column 'Status' (value: Completers, Total) before column Visit.

**TABLE 14.2-2.1.4 SUMMARY OF RELATIVE CHANGE FROM BASELINE OF IGF-1  
SERUM LEVELS (NMOL/L) BY COMPLETERS, TOTAL AND VISIT (FAS)**

See shell for TABLE 14.2-1.1.1 SUMMARY OF HEIGHT BY COMPLETERS, TOTAL AND VISIT (FAS).

Programming note: Please add one column 'Status' (value: Completers, Total) before column Visit.

**TABLE 14.2-2.2.1 ANALYSIS OF MEAN CHANGE FROM BASELINE IN IGF-1 SERUM LEVELS (NMOL/L) BY COMPLETERS, TOTAL AND VISIT (FAS)**

See shell for TABLE 14.2-1.2.1 ANALYSIS OF MEAN CHANGE FROM BASELINE IN HEIGHT BY COMPLETERS, TOTAL AND VISIT (FAS).

Programming note: Please add one column 'Status' (value: Completers, Total) before column Visit.

**TABLE 14.2-2.2.2 ANALYSIS OF MEAN CHANGE FROM BASELINE IN IGF-1 SERUM LEVELS (NMOL/L) BY COMPLETERS, TOTAL, VISIT AND SEX (FAS)**

See shell for TABLE 14.2-1.2.2 ANALYSIS OF MEAN CHANGE FROM BASELINE IN HEIGHT BY COMPLETERS, TOTAL, VISIT AND SEX (FAS).

Programming note: Please add one column 'Status' (value: Completers, Total) before column Visit.

**TABLE 14.2-2.2.3 ANALYSIS OF MEAN CHANGE FROM BASELINE IN IGF-1 SERUM LEVELS (NMOL/L) BY COMPLETERS, TOTAL, VISIT AND INITIAL TREATMENT (FAS)**

See shell for TABLE 14.2-1.2.3 ANALYSIS OF MEAN CHANGE FROM BASELINE IN HEIGHT BY COMPLETERS, TOTAL, VISIT AND INITIAL TREATMENT (FAS).

Programming note: Please add one column 'Status' (value: Completers, Total) before column Visit.

**TABLE 14.2-2.3.1 SUMMARY OF IGFBP-3 SERUM LEVELS (NMOL/L) BY COMPLETERS, TOTAL AND VISIT (FAS)**

See shell for TABLE 14.2-1.1.1 SUMMARY OF HEIGHT BY COMPLETERS, TOTAL AND VISIT (FAS).

Programming note: Please add one column 'Status' (value: Completers, Total) before column Visit. Please add confidence interval for means here.

**TABLE 14.2-2.3.2 SUMMARY OF IGFBP-3 SERUM LEVELS (NMOL/L) BY  
COMPLETERS, TOTAL, VISIT AND SEX (FAS)**

See shell for TABLE 14.2-1.1.2 SUMMARY OF HEIGHT BY COMPLETERS, TOTAL, VISIT AND SEX (FAS).

Programming note: Please add one column 'Status' (value: Completers, Total) before column Visit. Please add confidence interval for means here.

**TABLE 14.2-2.3.3 SUMMARY OF IGFBP-3 SERUM LEVELS (NMOL/L) BY  
COMPLETERS, TOTAL, VISIT AND INITIAL TREATMENT (FAS)**

See shell for TABLE 14.2-1.1.3 SUMMARY OF HEIGHT BY COMPLETERS, TOTAL, VISIT AND INITIAL TREATMENT (FAS).

Programming note: Please add one column 'Status' (value: Completers, Total) before column Visit.

**TABLE 14.2-2.3.4 SUMMARY OF RELATIVE CHANGE FROM BASELINE OF IGFBP-3  
SERUM LEVELS (NMOL/L) BY COMPLETERS, TOTAL AND VISIT (FAS)**

See shell for TABLE 14.2-1.1.1 SUMMARY OF HEIGHT BY COMPLETERS, TOTAL AND VISIT (FAS).

Programming note: Please add one column 'Status' (value: Completers, Total) before column Visit.

**TABLE 14.2-2.4.1 ANALYSIS OF MEAN CHANGE FROM BASELINE IN IGFBP-3 SERUM  
LEVELS (NMOL/L) BY COMPLETERS, TOTAL AND VISIT (FAS)**

See shell for TABLE 14.2-1.2.1 ANALYSIS OF MEAN CHANGE FROM BASELINE IN HEIGHT BY COMPLETERS, TOTAL AND VISIT (FAS).

Programming note: Please add one column 'Status' (value: Completers, Total) before column Visit.

**TABLE 14.2-2.4.2 ANALYSIS OF MEAN CHANGE FROM BASELINE IN IGFBP-3 SERUM  
LEVELS (NMOL/L) BY COMPLETERS, TOTAL, VISIT AND SEX (FAS)**

See shell for TABLE 14.2-1.2.2 ANALYSIS OF MEAN CHANGE FROM BASELINE IN HEIGHT BY COMPLETERS, TOTAL, VISIT AND SEX (FAS).

Programming note: Please add one column 'Status' (value: Completers, Total) before column Visit.

**TABLE 14.2-2.4.3 ANALYSIS OF MEAN CHANGE FROM BASELINE IN IGFBP-3 SERUM LEVELS (NMOL/L) BY COMPLETERS, TOTAL, VISIT AND INITIAL TREATMENT (FAS)**

See shell for TABLE 14.2-1.2.3 ANALYSIS OF MEAN CHANGE FROM BASELINE IN HEIGHT BY COMPLETERS, TOTAL, VISIT AND INITIAL TREATMENT (FAS).

Programming note: Please add one column 'Status' (value: Completers, Total) before column Visit.

**TABLE 14.2-2.5 SHIFT TABLE FOR IGF-1 BY COMPLETERS AND TOTAL (FAS)**

Programming note: Please add one column ‘Status’ (value: Completers, Total) before column Comparison.

**TABLE 14.2-2.6 SHIFT TABLE FOR IGFBP-3 BY COMPLETERS AND TOTAL (FAS)**

Programming note: Please add one column ‘Status’ (value: Completers, Total) before column Comparison.

**TABLE 14.2-2.7 SHIFT TABLE FOR IGF-1 IN PATIENTS WITH POWDER TREATMENT BY COMPLETERS AND TOTAL (FAS)**

Programming note: Please add one column ‘Status’ (value: Completers, Total) before column Comparison.

**TABLE 14.2-2.8 SHIFT TABLE FOR IGFBP-3 IN PATIENTS WITH POWDER TREATMENT BY COMPLETERS AND TOTAL (FAS)**

Programming note: Please add one column ‘Status’ (value: Completers, Total) before column Comparison.

**TABLE 14.2-2.9 SHIFT TABLE FOR IGF-1 IN PATIENTS WITH SOLUTION TREATMENT BY COMPLETERS AND TOTAL (FAS)**

Programming note: Please add one column ‘Status’ (value: Completers, Total) before column Comparison.

**TABLE 14.2-2.10 SHIFT TABLE FOR IGFBP-3 IN PATIENTS WITH SOLUTION TREATMENT BY COMPLETERS AND TOTAL (FAS)**

Comparison (Compared vs Baseline)	Baseline	Compared Visit				
		Low	Normal	High	Missing	Total
V02 vs V01	Low	XX	XX	XX	XX	XX
	Normal	XX	XX	XX	XX	XX
	High	XX	XX	XX	XX	XX
	Missing	XX	XX	XX	XX	XX
	Total	XX	XX	XX	XX	XX

Comparison (Compared vs Baseline)	Baseline	Compared Visit				
		Low	Normal	High	Missing	Total
V03 vs V02	Low	XX	XX	XX	XX	XX
	Normal	XX	XX	XX	XX	XX
	High	XX	XX	XX	XX	XX
	Missing	XX	XX	XX	XX	XX
	Total	XX	XX	XX	XX	XX
V.. vs V..	Low	XX	XX	XX	XX	XX
	Normal	XX	XX	XX	XX	XX
	High	XX	XX	XX	XX	XX
	Missing	XX	XX	XX	XX	XX
	Total	XX	XX	XX	XX	XX

Programming note: Please add one column 'Status' (value: Completers, Total) before column Comparison.

**TABLE 14.2-2.11.1 SUMMARY OF IGF-1/IGFBP-3 RATIO (NG/MCG) BY COMPLETERS, TOTAL AND VISIT (FAS)**

See shell for TABLE 14.2-1.1.1 SUMMARY OF HEIGHT BY COMPLETERS, TOTAL AND VISIT (FAS).

Programming note: Please add one column 'Status' (value: Completers, Total) before column Visit

**TABLE 14.2-2.11.2 SUMMARY OF IGF-1/IGFBP-3 RATIO (NG/MCG) BY COMPLETERS, TOTAL, VISIT AND SEX (FAS)**

See shell for TABLE 14.2-1.1.2 SUMMARY OF HEIGHT BY COMPLETERS, TOTAL, VISIT AND SEX (FAS).

Programming note: Please add one column 'Status' (value: Completers, Total) before column Visit

**TABLE 14.2-2.11.3 SUMMARY OF IGF-1/IGFBP-3 RATIO (NG/MCG) BY COMPLETERS, TOTAL, VISIT AND INITIAL TREATMENT (FAS)**

See shell for TABLE 14.2-1.1.3 SUMMARY OF HEIGHT BY COMPLETERS, TOTAL, VISIT AND INITIAL TREATMENT (FAS).

Programming note: Please add one column 'Status' (value: Completers, Total) before column Visit.

**TABLE 14.2-2.12.1 ANALYSIS OF MEAN CHANGE FROM BASELINE IN IGF-1/IGFBP-3 RATIO (NG/MCG) BY COMPLETERS, TOTAL AND VISIT (FAS)**

See shell for TABLE 14.2-1.2.1 ANALYSIS OF MEAN CHANGE FROM BASELINE IN HEIGHT BY COMPLETERS, TOTAL AND VISIT (FAS).

Programming note: Please add one column 'Status' (value: Completers, Total) before column Visit.

**TABLE 14.2-2.12.2 ANALYSIS OF MEAN CHANGE FROM BASELINE IN IGF-1/IGFBP-3 RATIO (NG/MCG) BY VISIT AND SEX (FAS)**

See shell for TABLE 14.2-1.2.2 ANALYSIS OF MEAN CHANGE FROM BASELINE IN HEIGHT BY COMPLETERS, TOTAL, VISIT AND SEX (FAS).

Programming note: Please add one column 'Status' (value: Completers, Total) before column Visit.

**TABLE 14.2-2.12.3 ANALYSIS OF MEAN CHANGE FROM BASELINE IN IGF-1/IGFBP-3 RATIO (NG/MCG) BY COMPLETERS, TOTAL, VISIT AND INITIAL TREATMENT (FAS)**

See shell for TABLE 14.2-1.2.3 ANALYSIS OF MEAN CHANGE FROM BASELINE IN HEIGHT BY COMPLETERS, TOTAL, VISIT AND INITIAL TREATMENT (FAS).

Programming note: Please add one column 'Status' (value: Completers, Total) before column Visit.

**TABLE 14.2-2.13.1 SUMMARY OF IGF-1 SDS BY COMPLETERS, TOTAL AND VISIT (FAS)**

See shell for TABLE 14.2-1.1.1 SUMMARY OF HEIGHT BY COMPLETERS, TOTAL AND VISIT (FAS).

Programming note: Please add one column 'Status' (value: Completers, Total) before column Visit. Please add confidence interval for means here.

**TABLE 14.2-2.13.2 SUMMARY OF IGF-1 SDS BY COMPLETERS, TOTAL, VISIT AND SEX (FAS)**

See shell for TABLE 14.2-1.1.2 SUMMARY OF HEIGHT BY COMPLETERS, TOTAL, VISIT AND SEX (FAS).

Programming note: Please add one column 'Status' (value: Completers, Total) before column Visit.

**TABLE 14.2-2.13.3 SUMMARY OF IGF-1 SDS BY COMPLETERS, TOTAL, VISIT AND INITIAL TREATMENT (FAS)**

See shell for TABLE 14.2-1.1.3 SUMMARY OF HEIGHT BY COMPLETERS, TOTAL, VISIT AND INITIAL TREATMENT (FAS).

Programming note: Please add one column 'Status' (value: Completers, Total) before column Visit.

**TABLE 14.2-2.14.1 ANALYSIS OF MEAN CHANGE FROM BASELINE IN IGF-1 SDS BY COMPLETERS, TOTAL AND VISIT (FAS)**

See shell for TABLE 14.2-1.2.1 ANALYSIS OF MEAN CHANGE FROM BASELINE IN HEIGHT BY COMPLETERS, TOTAL AND VISIT (FAS).

Programming note: Please add one column 'Status' (value: Completers, Total) before column Visit.

**TABLE 14.2-2.14.2 ANALYSIS OF MEAN CHANGE FROM BASELINE IN IGF-1 SDS BY COMPLETERS, TOTAL, VISIT AND SEX (FAS)**

See shell for TABLE 14.2-1.2.2 ANALYSIS OF MEAN CHANGE FROM BASELINE IN HEIGHT BY COMPLETERS, TOTAL, VISIT AND SEX (FAS).

Programming note: Please add one column 'Status' (value: Completers, Total) before column Visit.

**TABLE 14.2-2.14.3 ANALYSIS OF MEAN CHANGE FROM BASELINE IN IGF-1 SDS BY COMPLETERS, TOTAL, VISIT AND INITIAL TREATMENT (FAS)**

See shell for TABLE 14.2-1.2.3 ANALYSIS OF MEAN CHANGE FROM BASELINE IN HEIGHT BY COMPLETERS, TOTAL, VISIT AND INITIAL TREATMENT (FAS).

Programming note: Please add one column 'Status' (value: Completers, Total) before column Visit.

**TABLE 14.2-2.15.1 SUMMARY OF IGFBP-3 SDS BY COMPLETERS, TOTAL AND VISIT (FAS)**

See shell for TABLE 14.2-1.1.1 SUMMARY OF HEIGHT BY COMPLETERS, TOTAL AND VISIT (FAS).

Programming note: Please add one column 'Status' (value: Completers, Total) before column Visit. Please add confidence interval for means here.

**TABLE 14.2-2.15.2 SUMMARY OF IGFBP-3 SDS BY COMPLETERS, TOTAL, VISIT AND SEX (FAS)**

See shell for TABLE 14.2-1.1.2 SUMMARY OF HEIGHT BY COMPLETERS, TOTAL, VISIT AND SEX (FAS).

Programming note: Please add one column 'Status' (value: Completers, Total) before column Visit.

**TABLE 14.2-2.15.3 SUMMARY OF IGFBP-3 SDS BY COMPLETERS, TOTAL, VISIT AND INITIAL TREATMENT (FAS)**

See shell for TABLE 14.2-1.1.3 SUMMARY OF HEIGHT BY COMPLETERS, TOTAL, VISIT AND INITIAL TREATMENT (FAS).

Programming note: Please add one column 'Status' (value: Completers, Total) before column Visit.

**TABLE 14.2-2.16.1 ANALYSIS OF MEAN CHANGE FROM BASELINE IN IGFBP-3 SDS BY COMPLETERS, TOTAL AND VISIT (FAS)**

See shell for TABLE 14.2-1.2.1 ANALYSIS OF MEAN CHANGE FROM BASELINE IN HEIGHT BY COMPLETERS, TOTAL AND VISIT (FAS).

Programming note: Please add one column 'Status' (value: Completers, Total) before column Visit.

**TABLE 14.2-2.16.2 ANALYSIS OF MEAN CHANGE FROM BASELINE IN IGFBP-3 SDS BY COMPLETERS, TOTAL, VISIT AND SEX (FAS)**

See shell for TABLE 14.2-1.2.2 ANALYSIS OF MEAN CHANGE FROM BASELINE IN HEIGHT BY COMPLETERS, TOTAL, VISIT AND SEX (FAS).

Programming note: Please add one column 'Status' (value: Completers, Total) before column Visit.

**TABLE 14.2-2.16.3 ANALYSIS OF MEAN CHANGE FROM BASELINE IN IGFBP-3 SDS BY COMPLETERS, TOTAL, VISIT AND INITIAL TREATMENT (FAS)**

See shell for TABLE 14.2-1.2.3 ANALYSIS OF MEAN CHANGE FROM BASELINE IN HEIGHT BY COMPLETERS, TOTAL, VISIT AND INITIAL TREATMENT (FAS).

Programming note: Please add one column 'Status' (value: Completers, Total) before column Visit.

**TABLE 14.2-2.17.1 SUMMARY OF IGF-1/IGFBP-3 RATIO SDS BY COMPLETERS, TOTAL AND VISIT (FAS)**

See shell for TABLE 14.2-1.1.1 SUMMARY OF HEIGHT BY COMPLETERS, TOTAL AND VISIT (FAS).

Programming note: Please add one column 'Status' (value: Completers, Total) before column Visit.

**TABLE 14.2-2.17.2 SUMMARY OF IGF-1/IGFBP-3 RATIO SDS BY COMPLETERS, TOTAL AND VISIT AND SEX (FAS)**

See shell for TABLE 14.2-1.1.2 SUMMARY OF HEIGHT BY COMPLETERS, TOTAL, VISIT AND SEX (FAS).

Programming note: Please add one column 'Status' (value: Completers, Total) before column Visit.

**TABLE 14.2-2.17.3 SUMMARY OF IGF-1/IGFBP-3 RATIO SDS BY COMPLETERS, TOTAL, VISIT AND INITIAL TREATMENT (FAS)**

See shell for TABLE 14.2-1.1.3 SUMMARY OF HEIGHT BY COMPLETERS, TOTAL, VISIT AND INITIAL TREATMENT (FAS).

Programming note: Please add one column 'Status' (value: Completers, Total) before column Visit.

**TABLE 14.2-2.18.1 ANALYSIS OF MEAN CHANGE FROM BASELINE IN IGF-1/IGFBP-3 RATIO SDS BY COMPLETERS, TOTAL AND VISIT (FAS)**

See shell for TABLE 14.2-1.2.1 ANALYSIS OF MEAN CHANGE FROM BASELINE IN HEIGHT BY COMPLETERS, TOTAL AND VISIT (FAS).

Programming note: Please add one column 'Status' (value: Completers, Total) before column Visit.

**TABLE 14.2-2.18.2 ANALYSIS OF MEAN CHANGE FROM BASELINE IN IGF-1/IGFBP-3 RATIO SDS BY COMPLETERS, TOTAL, VISIT AND SEX (FAS)**

See shell for TABLE 14.2-1.2.2 ANALYSIS OF MEAN CHANGE FROM BASELINE IN HEIGHT BY COMPLETERS, TOTAL, VISIT AND SEX (FAS).

Programming note: Please add one column 'Status' (value: Completers, Total) before column Visit.

**TABLE 14.2-2.18.3 ANALYSIS OF MEAN CHANGE FROM BASELINE IN IGF-1/IGFBP-3 RATIO SDS BY COMPLETERS, TOTAL, VISIT AND INITIAL TREATMENT (FAS)**

[figure not shown]
See shell for TABLE 14.2-1.2.3 ANALYSIS OF MEAN CHANGE FROM BASELINE IN HEIGHT BY COMPLETERS, TOTAL, VISIT AND INITIAL TREATMENT (FAS).

Programming note: Please add one column 'Status' (value: Completers, Total) before column Visit.

**TABLE 14.2-3.1 SUMMARY OF THE DEVELOPMENT OF [REDACTED] HEIGHT AGE IN COMPARISON WITH CHRONOLOGICAL AGE BY COMPLETERS AND TOTAL (FAS)**

	Visit	by	N	N miss	Mean	SD	Min	Q1	Median	Q3	Max
Chronological age* (years)	V01	Males	XX	XX	XX.XX	X.XX	XX.X	XX.X	XX.X	XX.X	XX.X
		Females	XX	XX	XX.XX	X.XX	XX.X	XX.X	XX.X	XX.X	XX.X
		Powder	XX	XX	XX.XX	X.XX	XX.X	XX.X	XX.X	XX.X	XX.X
		Solution	XX	XX	XX.XX	X.XX	XX.X	XX.X	XX.X	XX.X	XX.X
		Total	XX	XX	XX.XX	X.XX	XX.X	XX.X	XX.X	XX.X	XX.X
	V05	Males	XX	XX	XX.XX	X.XX	XX.X	XX.X	XX.X	XX.X	XX.X

	Females	XX	XX	XX.XX	X.XX	XX.X	XX.X	XX.X	XX.X	XX.X	XX.X
	Powder	XX	XX	XX.XX	X.XX	XX.X	XX.X	XX.X	XX.X	XX.X	XX.X
	Solution	XX	XX	XX.XX	X.XX	XX.X	XX.X	XX.X	XX.X	XX.X	XX.X
	Total	XX	XX	XX.XX	X.XX	XX.X	XX.X	XX.X	XX.X	XX.X	XX.X
...	Males	XX	XX	XX.XX	X.XX	XX.X	XX.X	XX.X	XX.X	XX.X	XX.X
	Females	XX	XX	XX.XX	X.XX	XX.X	XX.X	XX.X	XX.X	XX.X	XX.X
	Powder	XX	XX	XX.XX	X.XX	XX.X	XX.X	XX.X	XX.X	XX.X	XX.X
	Solution	XX	XX	XX.XX	X.XX	XX.X	XX.X	XX.X	XX.X	XX.X	XX.X
	Total	XX	XX	XX.XX	X.XX	XX.X	XX.X	XX.X	XX.X	XX.X	XX.X

Height age§ (years)	V01^	Males	XX	XX	XX.XX	X.XX	XX.X	XX.X	XX.X	XX.X	XX.X
		Females	XX	XX	XX.XX	X.XX	XX.X	XX.X	XX.X	XX.X	XX.X
		Powder	XX	XX	XX.XX	X.XX	XX.X	XX.X	XX.X	XX.X	XX.X
		Solution	XX	XX	XX.XX	X.XX	XX.X	XX.X	XX.X	XX.X	XX.X
		Total	XX	XX	XX.XX	X.XX	XX.X	XX.X	XX.X	XX.X	XX.X
	V05&	Males	XX	XX	XX.XX	X.XX	XX.X	XX.X	XX.X	XX.X	XX.X
		Females	XX	XX	XX.XX	X.XX	XX.X	XX.X	XX.X	XX.X	XX.X
		Powder	XX	XX	XX.XX	X.XX	XX.X	XX.X	XX.X	XX.X	XX.X
		Solution	XX	XX	XX.XX	X.XX	XX.X	XX.X	XX.X	XX.X	XX.X
		Total	XX	XX	XX.XX	X.XX	XX.X	XX.X	XX.X	XX.X	XX.X

...	Males	XX	XX	XX.XX	X.XX	XX.X	XX.X	XX.X	XX.X	XX.X	XX.X
	Females	XX	XX	XX.XX	X.XX	XX.X	XX.X	XX.X	XX.X	XX.X	XX.X
	Powder	XX	XX	XX.XX	X.XX	XX.X	XX.X	XX.X	XX.X	XX.X	XX.X
	Solution	XX	XX	XX.XX	X.XX	XX.X	XX.X	XX.X	XX.X	XX.X	XX.X
	Total	XX	XX	XX.XX	X.XX	XX.X	XX.X	XX.X	XX.X	XX.X	XX.X

\* Chronological age determined using date of x-ray

[REDACTED]

^ Height age determined using height data from the measurement performed closest to pretreatment x-ray date

[REDACTED]

Programming note: Please add one column 'Status' (value: Completers, Total) before column Visit.

**TABLE 14.2-3.2 ANALYSIS OF MEAN CHANGE FROM BASELINE IN [REDACTED] AND HEIGHT AGE BY COMPLETERS AND TOTAL (FAS)**

Parameter	Difference between visits	by	N	Mean difference	95% Confidence interval for mean difference
Height age (years)	V05 - V01				
		Males	XX	X.XX	[ X.XX; X.XX ]
		Females	XX	X.XX	[ X.XX; X.XX ]
		Powder	XX	X.XX	[ X.XX; X.XX ]
		Solution	XX	X.XX	[ X.XX; X.XX ]
		Total	XX	X.XX	[ X.XX; X.XX ]
	...	Males	XX	X.XX	[ X.XX; X.XX ]
		Females	XX	X.XX	[ X.XX; X.XX ]
		Powder	XX	X.XX	[ X.XX; X.XX ]
		Solution	XX	X.XX	[ X.XX; X.XX ]
		Total	XX	X.XX	[ X.XX; X.XX ]

Programming note: Please add one column 'Status' (value: Completers, Total) before column Parameter.

**TABLE 14.2-3.3 SUMMARY OF THE MEAN RATIOS FOR THE COMPARISON OF CHANGES IN ██████████ HEIGHT AGE, AND CHRONOLOGICAL AGE (FAS)**

		Individual ratio of changes derived between visits	By	N	Missing	Mean	SD	Min	Q1	Median	Q3	Max	p-value #
████████ / ΔCA	V05 - V01	Males	XXX	XXX	X.XX	X.XX	X.X	X.X	X.XX	X.X	X.X	X.X	X.XXXX
		Females	XXX	XXX	X.XX	X.XX	X.X	X.X	X.XX	X.X	X.X	X.X	X.XXXX
		Powder	XXX	XXX	X.XX	X.XX	X.X	X.X	X.XX	X.X	X.X	X.X	X.XXXX
		Solution	XXX	XXX	X.XX	X.XX	X.X	X.X	X.XX	X.X	X.X	X.X	X.XXXX
		Total	XXX	XXX	X.XX	X.XX	X.X	X.X	X.XX	X.X	X.X	X.X	X.XXXX
	V.. - V01	Males	XXX	XXX	X.XX	X.XX	X.X	X.X	X.XX	X.X	X.X	X.X	X.XXXX
		Females	XXX	XXX	X.XX	X.XX	X.X	X.X	X.XX	X.X	X.X	X.X	X.XXXX
		Powder	XXX	XXX	X.XX	X.XX	X.X	X.X	X.XX	X.X	X.X	X.X	X.XXXX
		Solution	XXX	XXX	X.XX	X.XX	X.X	X.X	X.XX	X.X	X.X	X.X	X.XXXX
		Total	XXX	XXX	X.XX	X.XX	X.X	X.X	X.XX	X.X	X.X	X.X	X.XXXX
ΔHA / ΔCA	V05 - V01	Males	XXX	XXX	X.XX	X.XX	X.X	X.X	X.XX	X.X	X.X	X.X	X.XXXX
		Females	XXX	XXX	X.XX	X.XX	X.X	X.X	X.XX	X.X	X.X	X.X	X.XXXX
		Powder	XXX	XXX	X.XX	X.XX	X.X	X.X	X.XX	X.X	X.X	X.X	X.XXXX
		Solution	XXX	XXX	X.XX	X.XX	X.X	X.X	X.XX	X.X	X.X	X.X	X.XXXX
		Total	XXX	XXX	X.XX	X.XX	X.X	X.X	X.XX	X.X	X.X	X.X	X.XXXX
	V.. - V01	Males	XXX	XXX	X.XX	X.XX	X.X	X.X	X.XX	X.X	X.X	X.X	X.XXXX
		Females	XXX	XXX	X.XX	X.XX	X.X	X.X	X.XX	X.X	X.X	X.X	X.XXXX
		Powder	XXX	XXX	X.XX	X.XX	X.X	X.X	X.XX	X.X	X.X	X.X	X.XXXX
		Solution	XXX	XXX	X.XX	X.XX	X.X	X.X	X.XX	X.X	X.X	X.X	X.XXXX
		Total	XXX	XXX	X.XX	X.XX	X.X	X.X	X.XX	X.X	X.X	X.X	X.XXXX

		Individual ratio of changes derived between visits	By	N	Missing	Mean	SD	Min	Q1	Median	Q3	Max	p-value #
		Total	XXX	XXX	X.XX	X.XX	X.X	X.X	X.XX	X.X	X.X	X.X	X.XXXX
ΔHA / [REDACTED]	V.. - V01	Males	XXX	XXX	X.XX	X.XX	X.X	X.X	X.XX	X.X	X.X	X.X	X.XXXX
		Females	XXX	XXX	X.XX	X.XX	X.X	X.X	X.XX	X.X	X.X	X.X	X.XXXX
		Powder	XXX	XXX	X.XX	X.XX	X.X	X.X	X.XX	X.X	X.X	X.X	X.XXXX
		Solution	XXX	XXX	X.XX	X.XX	X.X	X.X	X.XX	X.X	X.X	X.X	X.XXXX
		Total	XXX	XXX	X.XX	X.XX	X.X	X.X	X.XX	X.X	X.X	X.X	X.XXXX
	V09 - V01	Males	XXX	XXX	X.XX	X.XX	X.X	X.X	X.XX	X.X	X.X	X.X	X.XXXX
		Females	XXX	XXX	X.XX	X.XX	X.X	X.X	X.XX	X.X	X.X	X.X	X.XXXX
		Powder	XXX	XXX	X.XX	X.XX	X.X	X.X	X.XX	X.X	X.X	X.X	X.XXXX
		XXX	XXX	X.XX	X.XX	X.X	X.XX	X.X	X.X	X.X	X.X	X.X	XXX
		XXX	XXX	X.XX	X.XX	X.X	X.XX	X.X	X.X	X.X	X.X	X.X	XXX

[REDACTED]; HA - Height Age; CA - Chronological Age  
# two-sided p-value for t-test with null hypothesis that ratio equals 1

Programming note: Please add one column 'Status' (value: Completers, Total) before first column.

TABLE 14.2-3.4 SUMMARY OF OVERWEIGHT PATIENTS BY SEX AND VISIT (FAS)

Sex	Visit	Total	Missing	N	Number of patients (%)	
					Normal	Overweight*
Male	Baseline	XXX	XXX	XXX	XXX (XX.X%)	XXX (XX.X%)
	V02	XXX	XXX	XXX	XXX (XX.X%)	XXX (XX.X%)
	...					
Female	Baseline	XXX	XXX	XXX	XXX (XX.X%)	XXX (XX.X%)
	V02	XXX	XXX	XXX	XXX (XX.X%)	XXX (XX.X%)
	...					
Total	Baseline	XXX	XXX	XXX	XXX (XX.X%)	XXX (XX.X%)
	V02	XXX	XXX	XXX	XXX (XX.X%)	XXX (XX.X%)
	...					

\* Defined by international cut off points for BMI for overweight by sex and age at visit. The cut-off point is defined by the percentile that passes through BMI at 25 kg/m^2 at age 18.

## 5.3 Figures

**FIGURE 14.2-1.11 Mean body height over time by completer, means  $\pm$  95% CI (FAS)**

**FIGURE 14.2-1.11.1 Mean body height over time by completer and sex, means  $\pm$  95% CI (FAS)**

**FIGURE 14.2-1.12 Mean H SDS over time by completer, means  $\pm$  95% CI (FAS)**

**FIGURE 14.2-1.12.1 Mean H SDS over time for patients with and without positive anti-rhGH antibodies, means  $\pm$  95% CI (FAS)**

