#### **10.4.2 Immunogenicity**

Subjects will be screened for anti-rhGH antibodies (ABs) at baseline, at 3, 6, 9, 12, 18 and 24 months, then annually during treatment, and at the end of treatment. For each time point the number and percentage of patients with anti-rhGH antibodies (ABs) will be tabulated.

Antibody-induced lack or loss of efficacy will be examined by comparing height outcome data between antibody-positive and antibody-negative subjects.

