#### **4.6.3 Immunogenicity**

All patients with a positive ADA result at any time during the study will be listed individually.

Tests for anti-rhGH antibodies were performed at baseline, at 3, 6, 9, 12 18 and 24 months, then annually during Omnitrope treatment and the end of treatment. As per protocol amendment 3, the anti HCP testing should be stopped after the amendment became effective in the respective country. Therefore, all HCP results since V01 will be presented up to the Visits occurred until the amendment 3 became effective. Number and percentage of patients with positive test for anti-hGH antibodies and anti-HCP antibodies will be provided by visit and overall (for anti-HCP antibodies).

In addition summary tables and figures for H SDS and HV SDS will be presented for patients with and without positive anti-rhGH antibody test.

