**TABLE 14.2-1.1.2 SUMMARY OF HEIGHT BY COMPLETERS, TOTAL, VISIT AND SEX (FAS)**

Visit	by	N	N miss	Mean	SD	Min	Q1	Median	Q3	Max
V01	Males	XX	XX	XXX.X	XX.X	XXX	XXX.X	XXX.X	XXX.X	XXX
	Females	XX	XX	XXX.X	XX.X	XXX	XXX.X	XXX.X	XXX.X	XXX
V02	Males	XX	XX	XXX.X	XX.X	XXX	XXX.X	XXX.X	XXX.X	XXX
	Females	XX	XX	XXX.X	XX.X	XXX	XXX.X	XXX.X	XXX.X	XXX
..	Males	XX	XX	XXX.X	XX.X	XXX	XXX.X	XXX.X	XXX.X	XXX
	Females	XX	XX	XXX.X	XX.X	XXX	XXX.X	XXX.X	XXX.X	XXX

Programming note: Please add one column 'Status' (value: Completers, Total) before column Visit.

Programming note: Please add confidence interval for means here.

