**TABLE 14.2-1.3.3 SUMMARY OF HSDS BY COMPLETERS, TOTAL, VISIT AND INITIAL TREATMENT (FAS)**

See shell for TABLE 14.2-1.1.3 SUMMARY OF HEIGHT BY COMPLETERS, TOTAL, VISIT AND INITIAL TREATMENT (FAS).

Programming note: Please add one column 'Status' (value: Completers, Total) before column Visit.

**TABLE 14.2-1.3.4 SUMMARY OF HSDS BY COMPLETERS, TOTAL, AND VISIT FOR PATIENTS WITH AND WITHOUT POSITIVE ANTI-RHGH ANTIBODIES (FAS)**

See shell for TABLE 14.2-1.1.2 SUMMARY OF HEIGHT BY COMPLETERS, TOTAL, VISIT AND SEX (FAS).

Programming note: Present patient with and without positive anti-rhGH antibodies instead of sex. Please add one column 'Status' (value: Completers, Total) before column Visit.

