**TABLE 14.2-1.4.1 ANALYSIS OF MEAN CHANGE FROM BASELINE IN HSDS BY COMPLETERS, TOTAL AND VISIT (FAS)**

See shell for TABLE 14.2-1.2.1 ANALYSIS OF MEAN CHANGE FROM BASELINE IN HEIGHT BY COMPLETERS, TOTAL AND VISIT (FAS).

Programming note: Please add one column 'Status' (value: Completers, Total) before column Visit.

**TABLE 14.2-1.4.2 ANALYSIS OF MEAN CHANGE FROM BASELINE IN HSDS BY  
COMPLETERS, TOTAL, VISIT AND SEX (FAS)**

See shell for TABLE 14.2-1.2.2 ANALYSIS OF MEAN CHANGE FROM BASELINE IN HEIGHT BY COMPLETERS, TOTAL, VISIT AND SEX (FAS).

Programming note: Please add one column 'Status' (value: Completers, Total) before column Visit.

**TABLE 14.2-1.4.3 ANALYSIS OF MEAN CHANGE FROM BASELINE IN HSDS BY  
COMPLETERS, TOTAL, VISIT AND INITIAL TREATMENT (FAS)**

Programming note: Please add one column 'Status' (value: Completers, Total) before column Visit.

See shell for TABLE 14.2-1.2.3 ANALYSIS OF MEAN CHANGE FROM BASELINE IN HEIGHT BY COMPLETERS, TOTAL, VISIT AND INITIAL TREATMENT (FAS).

Programming note: Please add one column 'Status' (value: Completers, Total) before column Visit.

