**FIGURE 14.2-1.13 Mean height velocity over time by completer, means  $\pm$  95% CI (FAS)**

**FIGURE 14.2-1.13.1 Mean height velocity over time by completer and sex, means  $\pm$  95% CI (FAS)**

**FIGURE 14.2-1.14 Mean HV SDS (cross-sectional) over time by completer, means  $\pm$  95% CI (FAS)**

**FIGURE 14.2-1.14.1 Mean HV SDS (cross-sectional) over time for patients with and without positive anti-rhGH antibodies, means  $\pm$  95% CI (FAS)**

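### Height SDS by antibody status is shown only as raw visit means, with no change-from-baseline or baseline-adjusted comparison, so a difference in starting height can be mistaken for, or hide, an antibody effect on cumulative gain

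*SAP*

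**What the plan says.** Protocol 10.4.2 sets the question: "Antibody-induced lack or loss of efficacy will be examined by comparing height outcome data between antibody-positive and antibody-negative subjects". It names no scale, no baseline adjustment and no test.

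SAP 4.6.3 answers it this way: "In addition summary tables and figures for H SDS and HV SDS will be presented for patients with and without positive anti-rhGH antibody test". Six outputs follow:

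- **Height SDS, raw values by visit:** Table 14.2-1.3.4 and Figure 14.2-1.12.1 ("Mean H SDS over time for patients with and without positive anti-rhGH antibodies"). The table borrows the shell of Table 14.2-1.1.2, with the programming note "Present patient with and without positive anti-rhGH antibodies instead of sex". That shell starts at V01.
- **Height velocity SDS, cross-sectional:** Table 14.2-1.7.4 and Figure 14.2-1.14.1 ("Mean HV SDS (cross-sectional) over time for patients with and without positive anti-rhGH antibodies").
- **Height velocity SDS, peak-centred:** Table 14.2-1.9.4 and Figure 14.2-1.15.1.

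Mean change from baseline in height SDS, with a 95% CI, is planned in Tables 14.2-1.4.1 (overall), 14.2-1.4.2 (by sex) and 14.2-1.4.3 (by initial treatment). No such table is planned by antibody status. No positive-minus-negative difference is estimated for any growth outcome.

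**The concern.** Lack or loss of efficacy is about height gained on treatment. A raw height SDS mean mixes the gain with the height a child started from. Antibody status is not randomised. If positives are few, their mean starting height SDS can differ from that of the negatives by chance alone.

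If positive children started taller, a real loss of effect could be hidden. If they started shorter, a harmless antibody could look like poor response.

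The plan also falls short of its own practice here. Protocol 10.5.1 judges effectiveness by comparison with baseline, and SAP 4.6.1 promises confidence intervals for the change from baseline in efficacy endpoints. Immunogenicity is a stated purpose of the study (Protocol, section 2), and this is the split for which the height SDS change table is missing.

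**Working it through.** The plan gives no sample size, power or decision rule for this comparison, so there is no figure of its own to reproduce. The check has three steps.

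**1. Which outputs exist**

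| Outcome | Overall, sex, initial treatment | Antibody status |
|---|---|---|
| Height SDS, raw by visit | Yes | Yes |
| Height SDS, change from baseline | Yes | No |
| Height velocity SDS, by visit | Yes | Yes (two versions) |

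Under SAP 4.6.1, height velocity up to month 12 is measured from height at the start of treatment. It therefore captures the whole on-treatment gain, annualised. From month 15 it uses the height 12 months earlier. After month 12, then, no output by antibody status shows within-child cumulative gain.

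**2. How large a chance difference at baseline could be**

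Inputs:
- N = 277, from the safety-set shell, Table 14.3-1.1. The growth outputs use the FAS; SAP 4.8 gives 278 treated, and using 278 leaves the two-decimal results unchanged.
- Number positive (n₊): not in the documents; assumed 5, 10 or 20.
- SD of baseline height SDS: not in the documents; assumed 0.5 to 0.8.

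Formula: SE = SD × √(1/n₊ + 1/(277 − n₊)); 95% chance limits = ±1.96 × SE.

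| n₊ | √(1/n₊ + 1/(277 − n₊)) | SE, SD 0.5 | SE, SD 0.8 | 95% limits |
|---|---|---|---|---|
| 5 | 0.451 | 0.226 | 0.361 | ±0.44 to ±0.71 |
| 10 | 0.322 | 0.161 | 0.258 | ±0.32 to ±0.51 |
| 20 | 0.232 | 0.116 | 0.186 | ±0.23 to ±0.36 |

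If positives were common, say 83 of 277 (30%), the limits with an SD of 0.4 to 0.8 fall to ±0.10 to ±0.21.

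For scale, the pooled report of four randomised studies cited in Protocol 1.2.3 gives a six-year gain of 2.0 SD at the low dose. Before rounding the limits run from 0.2275 to 0.708, and 0.2275/2.0 = 11% and 0.708/2.0 = 35%. These are outer limits, not expected values: one SE with 20 positives and an SD of 0.5 is 0.116/2.0, about 6%.

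**3. How much of it persists**

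Let d₀ be the baseline difference and b the slope of later height SDS on baseline height SDS (not given; assumed 0.6 to 1.0). With no true antibody effect, the raw comparison shows b × d₀ and the change from baseline shows (b − 1) × d₀. For d₀ = 0.5:

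| b | Raw | Change from baseline | Adjusted for baseline |
|---|---|---|---|
| 0.6 | 0.30 | −0.20 | 0 |
| 0.8 | 0.40 | −0.10 | 0 |
| 1.0 | 0.50 | 0.00 | 0 |

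Carry-over into the raw means is one-for-one only at b = 1. Change from baseline has the smaller artefact whenever b exceeds 0.5, but removes it fully only at b = 1. A linear adjustment for baseline removes it at any b.

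**The case against.** The strongest reply is that the plan does not rest on raw height SDS alone. Four of the six growth outputs by antibody status are height velocity SDS, built from within-child gain, so a starting difference is not carried directly into them. Height velocity SDS is also the protocol's own measure of treatment failure in year one (6.5.9). For a late loss of effect, a 12-month window may be more sensitive than cumulative change. This stands. It makes the gap small but does not close it, because cumulative gain after month 12 is still not shown.

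Second, the V01 means are printed in the same table, so a reader can see an imbalance and subtract it. This stands only in part. Children leave at final height or after a poor first year, so the V01 mean and a later mean describe different children. The completers rows do not cure this, since completers finish at different visits. Nor can a confidence interval for the change be recovered without the within-child correlation.

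Third, positive patients are listed individually (4.6.3), which suits a handful of cases. That helps with case review but gives no group estimate.

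A reader might infer three stronger things that the documents do not support:

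- **That efficacy loss is judged on raw height SDS and any difference will be read as an antibody effect.** The comparison is descriptive, with no test, threshold or rule.
- **That the full starting difference reaches every visit.** That needs a slope of 1.
- **That the raw intervals are wider than need be.** With equal variances, SD(change)/SD(raw) = √(2(1 − ρ)), which is below 1 only if the baseline-to-visit correlation ρ exceeds 0.5. The documents give no correlation.

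**Conclusion.** The point holds as a minor one, confined to height SDS. By antibody status the SAP plans raw visit means only, although it already tabulates change from baseline for every other planned split of this outcome. A starting difference can carry in whole or part into later visits and confuse the reading of cumulative gain after month 12. It does not invalidate the immunogenicity assessment.

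The size cannot be fixed from the documents. The limits of about ±0.23 to ±0.71 SDS rest wholly on an assumed 5 to 20 positives and SD of 0.5 to 0.8. They shrink if positives are more common. The entry criterion of height SDS below −2.5 also limits how much taller one group can start, though not how much shorter. When a child counts as antibody-positive is a separate question, not addressed here.

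**What to change.** - Add a Table 14.2-1.4.4: mean change from baseline in height SDS with 95% CI, by antibody status and visit, using the shell of Table 14.2-1.2.2 with antibody status in place of sex.
- Keep the raw curves in Figure 14.2-1.12.1, because they show any starting imbalance, and add a change-from-baseline panel beside them.
- At annual visits where the number of positives allows, report the positive-minus-negative difference in height SDS adjusted for baseline height SDS, with a 95% CI, labelled descriptive. State in the SAP the minimum number of positives for doing so. Below that number, the change table and the individual listing are enough.

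The cost is one table, one figure panel and a simple model, all from variables already derived. Only SAP wording changes; no new data are needed.
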